Previous coronavirus outbreaks have been associated with long-term symptoms like muscle weakness, pain, fatigue, depression, anxiety, pulmonary function impairment, vocational problems, and reduced quality of life [16-18]. Similarly, COVID-19 may have a lasting impact on physical, cognitive, mental, and social health, even in patients with mild disease presentation [19]. As acute symptoms improve and patients are exiting quarantine, they may be classified as hemodynamically stable and infection-free. Yet, many may still exhibit the physical (i.e., dyspnea, fatigue, weakness, pressure ulcers), cognitive (i.e., delirium), and emotional (i.e., depression) consequences of prolonged bed rest and quarantine, also known as post-intensive care syndrome [19]. These complications may lead to limited mobility, decreased independence in activities of daily living, re-hospitalization, and poor quality of life, all of which may be mitigated by early rehabilitation [20]. These lasting effects are also evidenced by recent studies [3,4] that assessed persistent symptoms in recently discharged COVID-19 patients and reported that decreased quality of life was observed among 44.1% and fatigue was still reported by 53.1% [3] to 71% [4] of patients. Importantly, both hospitalized and non-hospitalized patients showed persistent fatigue after acute COVID-19 infection [5].

Fatigue is “the decrease in physical and/or mental performance that results from changes in central, psychological, and/or peripheral factors” and significantly reduces one’s ability to participate in activities of daily living [21]. Many of the current treatments of fatigue, including pharmaceuticals, are only mildly effective and are often very expensive. Thus, a practical, inexpensive, and effective

adjunct treatment is urgently required. One possible modality that fulfills these requirements is transcranial direct current stimulation (tDCS) [22]. tDCS is a non-invasive means of increasing the excitability of targeted brain regions [9] and has been successfully used for several years in healthy populations [23] and in patients with neurological disorders to treat fatigue [24-27]. Recent studies have shown that tDCS intensities up to 4 mA are safe, tolerable, and do not elicit any serious adverse effects [24,28,29]. Additionally, tDCS can feasibly be delivered outside of a clinic setting [30], which may be of particular importance during a pandemic.

I.7

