tDCS TREATMENT PROTOCOL: A tDCS device (Soterix) will deliver a small direct current through two sponge surface electrodes (5 cm × 7 cm) soaked with ~15 mL of NaCl saline. The positive electrode (anode) will be placed over the M1 representation of the weaker leg (as determined by the strength test), and the return electrode (cathode) will be placed above the eyebrow on the opposite side of the head.

tDCS BLOCK: The participants will receive tDCS for 20 min while seated comfortably and quietly in a room. The intensity will start at 0 mA and will be incrementally increased to the target intensity of 4 mA over the initial 30 seconds. At the 20-minute time point, the current will be gradually reduced to 0 mA over 30 seconds.

SHAM BLOCK: During the sham block, stimulation will ramp up over 30 seconds, remain at the target intensity for 30 seconds, and then will ramp down over 30 seconds during the first and last 90 seconds of the 20 minute stimulation period. This sham protocol has previously been shown to improve subject blinding integrity.

Brain activity PET Imaging with [18F]Fluorodeoxyglucose (FDG): A subset of 10 subjects from each group will be asked to fast for a minimum of 6 hours prior to the FDG administration. The blood glucose level will be checked and must be less than or equal to 200 mg/dL in order to proceed with the imaging. FDG (5 mCi ± 10% IV) will be administered and tracer uptake will take place in a quiet, darkened room with eyes open and ears unplugged. Attenuation correction imaging (either AC-CT or transmission imaging) will be performed with emission imaging equivalent to that used in the ADNI-3 protocol.

FDG PET Image Processing: FDG images will be analyzed by volume-of-interest (VOI) based on the individual's structural MRI (maximum probability atlas of Neuro Tool of PMOD Biomedical Image Quantification, version 4.1, PMOD Technologies, Ltd., Zurich, Switzerland) as well as using currently-available software tools designed specifically for the analysis of FDG images (e.g., NeuroQ (Syntermed, Inc.), PALZ (PMOD Technologies, LTD), MIM6, Neuro tool (v.6.6, MIM Software, Inc.). Partial volume-corrected image data will also be analyzed. Global metabolism will be determined by calculating the volume-weighted average of the standardized uptake values (SUV) of the intracerebral pixels. Mean, median and partial volume-corrected mean SUVs will be determined for each tissue type (GM, WM), lobe, and region using the Neuro Tool (PMOD).

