Subjects who are part of the symptomatic group will be compensated \$120 for their time and effort upon completion of the first five visits of the study. Two follow-up visits will be compensated at \$25 per visit, for a total of \$170 for completion of the entire study. If the subjects withdraw before completing the entire study, they will be paid for each session they completed, as follows: blood draw/vascular assessment, \$30 each visit (\$60 total for baseline and post-tDCS testing), tDCS/SHAM sessions: \$15 each visit (\$60 total).

Subjects who are part of the asymptomatic group will be compensated \$35 for their time and effort upon completion of visit one.

VIII. Risks

VIII.1

What are the risks to subjects including

- ***emotional or psychological***
- ***financial***
- ***legal or social***
- ***physical?***

tDCS safety (only applicable to symptomatic participants): tDCS is a non-invasive brain stimulation technique in which a very weak electrical current is applied to the scalp. tDCS has been conducted on humans and animals for many years and no evidence has emerged to suggest that it is harmful or has ever induced a serious side effect. However, the safety of tDCS is dependent on current strength, electrode size, and stimulation duration. Accordingly, these parameters have been investigated to establish safe and effective stimulation parameters for tDCS applications in research involving human subjects. The only side effects that have been reported when proper guidelines are followed are a temporary headache, skin redness under the electrodes, and/or tingling, itching, and burning sensations in some subjects. For example, a 2008 review of the approximately 100 human tDCS studies up until that time on healthy adults and patients found that 64 of these studies reported no side effects, 24 studies reported a temporary itching or tingling under the electrodes in some subjects, and one study reported skin redness. Furthermore, these slight side effects were of equal occurrence in subjects that received placebo stimulation in 7 studies. In addition, only two subjects in these 100 studies reported a mild headache. Similar findings have recently

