been reported in research and review articles (Nitsche et al. 2008; Hummel et al. 2008). Physiological studies have also assessed the safety of tDCS when applied within the aforementioned stimulation guidelines. For example, there was no neuronal damage as measured by serum neuron-specific enolase (Stagg & Nitsche, 2011) or MRI measures of edema using contrast-enhanced and diffusion-weighted MRI measures following administration of tDCS (Nitsche et al. 2004). Furthermore, tDCS did not negatively alter measures of neuropsychological function and EEG activity (Iver et al. 2005). Accordingly, rat studies using tDCS models emulating tDCS applied to humans (Liebetanz et al. 2009) showed that the current density needed to induce tissue damage or lesions was about 1429 mA/cm^2 , whereas the current densities used in human studies are between 0.04 and 0.08 mA/cm^2 and in this proposal is 0.011 mA/cm^2 . In conclusion, the probability is very unlikely that harm may occur (see above). Based on the available literature a slight headache should be the worst possible negative effect and should be very rare. In this case, non-prescription medication should relieve the headache within 1-2 hours.

Risk of Blood Draw: Subjects may experience some discomfort/bleeding from the blood draws. Other risks include bruising and infection. To minimize these risks, all blood draws will be performed by certified personnel at the CRU in the University of Iowa Hospital.

Carotid-femoral pulse wave velocity (PWV) and flow-mediated dilation: There are no known or foreseeable risks associated with the use of carotid-femoral pulse wave velocity or flow-mediated dilation. ECG electrodes may cause minor irritation to the skin.

Risks of performing motor tasks: There is potential for injury (muscle strain) resulting from the strength, fatigue, and walking tests. There is a 0.01% chance of death (in people who have heart problems), a 0.02% risk of cardiac arrhythmias that would require the subjects to go to the hospital (in people with heart problems), and a risk of an increase or decrease in blood pressure. Following participation, subjects may experience some muscle soreness. Muscle soreness tends to be more common for individuals who have not exercised recently. Other risks may include feelings of anxiety and/or stress induced by the experiment, which can lead to an increase in heart rate and blood pressure.

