PET Imaging: This study involves the administration of a PET radiopharmaceutical, $[18\text{F}]$ fluorodeoxyglucose (FDG). FDG has been used at the University of Iowa and throughout the world for a variety of conditions. There have been a few reports of relatively rare side-effects involving temporary low blood pressure and allergic reactions. As a result of participating in this research, each subject will receive a dose of radiation equivalent to approximately 15% of the dose that a medical radiation worker can accrue yearly. FDG dose = $5 \pm 10\%$ mCi. Radiation dose = $110 \text{ mrem/mCi} = 605 \text{ mrem} + 180 \text{ mrem}$ for CT = $730 \text{ mrem} = \sim 15\%$ of dose for medical radiation worker. Although there are no proven harmful effects from the level of radiation exposure in this study, long-term effects on a subject's health cannot be ruled out with certainty. Pregnancy is a contraindication to PET imaging. Thus, all women of childbearing potential will undergo a pregnancy test before PET imaging. Injection of tracers will require the placement of an intravenous catheter. As in any procedures involving catheters placed in veins, there are several risks, including infection, clotting, or continued bleeding. There may also be bruising, skin irritation, and a dull ache at the site of injection. The subject will be asked to fast for a minimum of 6 hours prior to the FDG study. There is a small risk of hypoglycemia associated with this fast.

Risks of MRI:

Participants may be uncomfortable inside the MRI scanner if they do not like to be in closed spaces ("claustrophobia"). During the procedure, they will be able to talk with the MRI staff through a speaker system. Participants can stop the scan at any time.

The MRI scanner produces a loud hammering noise, which has produced hearing loss in a very small number of patients. Participants will be given noise-canceling headphones to reduce this risk. A metal object flying through the air toward the magnet and hitting the participants presents the greatest risk associated with MRI. To reduce this risk, we require that all people involved with the study remove all metal from their clothing and pockets. No metal objects will be brought into the magnet room while participants are inside the room. In addition, the door to the room will remain closed throughout the study so that no one can accidentally bring a metal object into the room.

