There are no known risks associated with limited exposure to magnetic fields. Magnets of this strength have been in use for medical imaging for over 15 years. However, we will keep a record of the length of time participants were in the magnet, as well as the amount of radio waves used during that time.

Risks of Pulse Wave Velocity

There are no known risks associated with the use of a non-invasive pulse transducer for pulse wave velocity. ECG electrodes may cause minor irritation to the skin.

Risks of Carotid Echocardiography

There are no known serious risks associated with the use of carotid echocardiography. ECG electrodes may cause minor irritation to the skin.

Risks of Brachial Artery FMD test

There is a risk of mild discomfort on the forearm when the blood pressure cuff is inflated and a mild temporary sensation of “pins and needles” in the forearm and hand. This feeling is completely reversed within several minutes after the cuff is released with no permanent discomfort.

Risk Cardiovagal Baroreflex Sensitivity test

There are no known risks associated with the use of this test.

Although the risk is minimal, there is a risk for breach of confidentiality.

VIII.2

What have you done to minimize the risks?

- ***If applicable to this study ALSO include:***
 - ***How you (members of your research team at Iowa) will monitor the safety of individual subjects.***
 - ***Include a description of the availability of medical or psychological resources that subjects might require as a consequence of participating in this research and how referral will occur if necessary (e.g. availability of emergency medical care, psychological counseling, etc.)***

All risks will be minimized by using safe, well-established procedures and strict monitoring of each experimental session. Study staff will be in close proximity to each subject to help prevent/minimize fall risk and muscle strain. Furthermore, risk will be minimized by using stimulation parameters that are well described, within international guidelines, and within the range of those used in hundreds, if not thousands, of studies (see above).

The venous catheter will be inserted by an individual from the PET Center that is qualified, trained, and experienced at inserting venous lines.

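### The risk section gives the tDCS current density as about one-tenth of its planned value, which turns an above-range exposure into a below-range one; the PET dose is mis-summed and covers one of at least two scans

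*Combined protocol and SAP*

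**What the plan says.** **Stimulation.** Section VII.E.6 (tDCS treatment protocol) delivers current through "two sponge surface electrodes (5 cm × 7 cm" each, with the current "incrementally increased to the target intensity of 4 mA over the initial 30 seconds". Section VIII.1 (tDCS safety) says that "the safety of tDCS is dependent on current strength, electrode size, and stimulation duration". It then compares densities. In rats, "the current density needed to induce tissue damage or lesions was about 1429 mA/cm^2"; for people, "current densities used in human studies are between 0.04 and 0.08 mA/cm^2 and in this proposal is 0.011 mA/cm^2". The next sentence concludes that harm is very unlikely. Section VIII.2 adds that the stimulation parameters are "within the range of those used in hundreds, if not thousands, of studies (see above").

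**PET.** Section VIII.1 (PET Imaging) says that "each subject will receive a dose of radiation equivalent to approximately 15% of the dose that a medical radiation worker can accrue yearly". It derives this from 5 mCi ± 10% of FDG at 110 mrem/mCi, written as 605 mrem, plus 180 mrem for CT, with a stated total of 730 mrem. Section VII.E.6 has PET in 10 subjects per group. It schedules the Day 5 scan for those who already had a scan before treatment.

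**The concern.** The stated density does not follow from the protocol's own current and electrode size, and the error runs in the favourable direction. As printed, the trial looks gentler than the human studies it is compared with. With the planned settings it is stronger than all of that quoted range. The protocol names current strength and electrode size as determinants of safety, and these are the two inputs to the figure.

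The IRB relies heavily on this section. There is no separate written protocol (VII.B.11). The device is not approved for this use and has no IDE (VII.B.24, VII.B.25), and non-significant-risk status is requested (VII.B.29). No periodic review of combined data is planned (VIII.3).

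For PET, the sum does not add up. A one-scan total is also presented as the dose from taking part in the study, although the imaged subjects are scanned more than once.

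**Working it through.** **Current density**

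Inputs: 4 mA and 5 cm × 7 cm = 35 cm² (VII.E.6); stated density 0.011 mA/cm², human range 0.04–0.08 mA/cm² and rat lesion figure 1429 mA/cm² (VIII.1).

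1. Density = current / electrode area = 4/35 = 0.114 mA/cm².
2. Attempts to reproduce 0.011: the combined area of both electrodes gives 4/70 = 0.057; 2 mA on one electrode gives 0.057; 1 mA gives 0.029. Only 0.4 mA, a tenfold slip, gives 0.4/35 = 0.0114. To reach 0.011 exactly would take 0.011 × 35 = 0.385 mA, or an electrode of 4/0.011 = 364 cm².
3. Size of the error: 0.1143/0.011 = 10.4.
4. Position against the quoted human range: as stated, 0.011/0.04 = 0.28 of the bottom; as planned, 0.1143/0.08 = 1.43 times the top. On a 35 cm² electrode the range equals 0.04 × 35 = 1.4 mA to 0.08 × 35 = 2.8 mA, so 4 mA cannot fall inside it.
5. Margin to the rat figure: 1429/0.1143 ≈ 12,500 as planned; 1429/0.011 ≈ 130,000 as stated.

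**PET dose**

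Inputs: 5 mCi ± 10%, 110 mrem/mCi, 180 mrem for CT, stated total 730 mrem ≈ 15% of a worker's yearly dose (VIII.1); at least two scans, before treatment and on Day 5 (VII.E.6).

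1. The printed sum: 605 + 180 = 785, not 730. The 605 is 5.5 × 110, the upper activity limit; the 730 is 5.0 × 110 + 180, the nominal activity. Two activities are mixed. The effect of this slip alone is 785/730 = 1.075, or 15% becoming 16%.
2. The yearly worker dose is not stated; the document's figures imply 730/0.15 ≈ 4,870 mrem. The percentages below use that scale.
3. Dose = number of scans × (mCi × 110 + 180):

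| Activity | One scan with CT | Two scans with CT | Ratio to 730 | % of implied yearly dose |
|---|---|---|---|---|
| 4.5 mCi | 675 mrem | 1,350 mrem | 1.85 | 28% |
| 5.0 mCi | 730 mrem | 1,460 mrem | 2.00 | 30% |
| 5.5 mCi | 785 mrem | 1,570 mrem | 2.15 | 32% |

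4. VII.E.6 allows transmission imaging in place of CT. FDG alone over two scans is then 2 × 495 = 990 to 2 × 605 = 1,210 mrem (1.36 to 1.66 times 730; 20% to 25%), plus a transmission dose that the document does not give.
5. VII.E.6 also says that the Day 1 and Day 5 battery is repeated at three and six weeks. It is unclear whether that includes PET, since the blood draw, also part of the battery, is budgeted for two occasions only. If PET were repeated at both follow-ups, four scans with CT at 5 mCi would give 4 × 730 = 2,920 mrem, or 60%.

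**The case against.** The best defence is that the safety case does not hang on this one number. The sentence mainly contrasts human use with the rat lesion figure, and that contrast survives by a factor of about 12,500. The conclusion also draws on a review of about 100 human studies and on biochemical, MRI, EEG and neuropsychological data. The non-significant-risk rationale (VII.B.31) cites earlier use of the device and two attachments, which are not available here. Section I.6 states that "tDCS intensities up to 4 mA are safe, tolerable, and do not elicit any serious adverse effects", and VII.B.32 lists prior studies, several at 4 mA. Current and electrode size are openly stated, and no endpoint, analysis or sample size is affected.

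Most of this stands as an argument that 4 mA may well be justified. It does not make the printed density, or the trial's place relative to the quoted range, correct. The back-reference in VIII.2 may point to the literature review and not to the density sentence. Even so, a statement that the parameters lie within the usual range conflicts with the only human density range the document gives.

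On PET, the summing slip is indeed small, and about 15% is fair for one scan. The phrase about each subject stands under the PET heading and may be meant for imaged subjects only. The Day 1 list in VII.E.6 and the compensation plan in VII.E.19 do not mention PET, so the imaging schedule itself needs confirming. Asymptomatic subjects finish after Day 1 and cannot have the Day 5 scan. Any separate radiation-committee submission is not visible. These points limit who receives the two-scan dose. They do not make a one-scan total right for those scanned twice, and Hypothesis 3, which concerns change in FDG uptake, needs two scans.

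**Conclusion.** The concern holds, and the risk section should be corrected. The planned density is 0.114 mA/cm², so the document understates it 10.4-fold and places the trial below a human range that it exceeds by 43% at the top. This rests only on the current and electrode size in VII.E.6. The range and the rat figure are taken as the document quotes them, because their sources could not be checked. The finding is not that 4 mA is unsafe; it is that this comparison cannot be used to support it.

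The PET point is secondary. For subjects imaged before treatment and on Day 5 with CT, the dose is about twice the stated one (1.85 to 2.15 times over the activity tolerance). Without CT it is 1.36 to 1.66 times from FDG alone. For subjects who are not imaged, the stated dose does not apply.

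**What to change.** - In VIII.1, replace 0.011 with 0.114 mA/cm² and state that this is above the 0.04–0.08 range quoted.
- In VIII.2, revise the statement that the parameters lie within the range of earlier studies so that it agrees.
- Support 4 mA with the 4 mA safety and tolerability work already cited in I.6 and VII.B.32.
- Restate the radiation dose as one consistent per-scan figure with CT (730 mrem at 5 mCi; 675–785 over ±10%), and give the transmission-imaging alternative. Multiply by the number of scheduled scans, and limit the statement to the imaged subset.
- Say which subjects are imaged and when, and whether the three- and six-week visits include PET.
- Carry the corrected figures into the consent form wherever they appear there.

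The cost is a text correction and notification of the IRB. No procedure, schedule or sample size changes. The density comparison and the dose for the imaged subset will read less favourably than they do now.

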
I.5 *Specify your research question(s), study aims or hypotheses (do not indicate "see protocol")*

The objective of this application is to investigate the short- and long-term effects of multiple sessions of 4 mA M1 tDCS on fatigue and brain activity in recovered COVID-19 patients using established measures of perception of fatigue, performance fatigability, and cerebral glucose uptake. Our central hypothesis is that tDCS will improve fatigue short- and long-term, and thus will improve quality of life (QOL) in recovered COVID-19 patients and that these changes will be associated with alterations in brain activity.

Aim 1: Determine the short-term effects of multiple sessions of M1 tDCS on fatigue, and the subsequent influence on QOL, in recovered COVID-19 patients.

Hypothesis 1: Fatigue and QOL will significantly improve immediately after five consecutive sessions of M1 tDCS.

Aim 2: Determine the long-term effects of multiple sessions of tDCS on fatigue and the subsequent influence on QOL, in recovered COVID-19 patients.

Hypothesis 2: The improvements in fatigue and QOL of recovered COVID-19 patients will be present at 3- and 6-week follow-ups.

Aim 3: Determine the association between cerebral glucose uptake and changes in fatigue/QOL measures in recovered COVID-19 patients.

Hypothesis 3: Changes in cerebral FDG uptake will be correlated with improved fatigue and quality of life.

Aim 4: Determine the effects of multiple sessions of tDCS on vascular function (arterial stiffness, endothelial function), baroreflex function, and cognitive function in recovered COVID-19 patients.

Hypothesis 4: Improvements in vascular function (arterial stiffness, endothelial function), baroreflex function, and cognitive function immediately after five consecutive sessions of M1 tDCS, and at 3 weeks and 6 weeks.

I.6 *Background and significance and/or Preliminary studies related to this project. (do not indicate "see protocol")*

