VII.B.6 *Will any subjects receive a placebo in this study when, if they were not participating, they could be receiving an FDA-approved treatment for their condition?*
No

VII.B.11 *Is there a separate, written protocol that will be submitted in addition to this IRB New Project form? (Note: a grant application is not considered to be a protocol)*
No

VII.B.18 *Does this project involve the evaluation, or testing, of the safety and/or efficacy of a medical device?*
Yes

VII.B.19 *Describe in detail procedures in place for maintaining device shipment and receipt records:*
N/A

VII.B.20 *Who will be responsible for maintaining these shipment and receipt records?*
N/A

VII.B.21 *Describe in detail procedures in place for tracking use and disposition of devices described in this study:*
N/A

VII.B.22 *Who will be responsible for maintaining these use and disposition tracking records?*
The PI

VII.B.23 *Describe in detail procedures in place to limit access to authorized study personnel for the storage, control, and dispensing of the investigational devices. (For example, investigational devices are kept in a locked area away from approved devices or have a keyed interlock, and only study personnel authorized to dispense the device have the keys)*
The device will be in a locked cabinet in the laboratory of the PI.

VII.B.24 *Is the device FDA-approved for the way it will be used in this study?*
No

VII.B.25 *Is there an IDE (Investigational Device Exemption) for this device in this research project?*
No

VII.B.29 *Indicate the appropriate FDA status you and/or the sponsor are requesting for the use of this device in this study.*
Non-Significant Risk (NSR) device/software

VII.B.31 *Provide a detailed rationale for why this device meets the FDA definition of a Non-Significant Risk Device (NSR)*
Numerous studies used this device without any serious side effects. See attachments "tDCS Safety" and "tDCS Tolerability."

VII.B.32 *Provide a summary of prior investigations with this device.*
The PI used this device in previous studies without any serious adverse side effects.

[name], [name], and [name] (2020). Transcranial Direct Current Stimulation (tDCS) for the Treatment of a Multiple Sclerosis Symptom Cluster. *Brain Stimulation* 13(1), 263-264.

[name], [name], and [name] (2020). The Tolerability and Efficacy of 4 mA Transcranial Direct Current Stimulation on Leg Muscle Fatigability. *Brain Sciences* 10(1), 12. IF: 3.332

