The data that will be shared with the Medical University of South Carolina (MUSC) will be de-identified, age, race and ethnicity will be reported as required by NIH (see attached template that will be requested for reporting purposes) as part of a final report to MUSC.

X.7

Does your study meet the NIH criteria for a Certificate of Confidentiality or will you be applying for Certificate of Confidentiality?

No

XI. Data Analysis

XI.1

Describe the analysis methods you will use, including, if applicable, the variables you will analyze

The generalized estimating equation (GEE) framework will be utilized to assess changes over time in fatigue and quality of life measures. An interaction term between time and treatment will allow us to test the within- and between-treatment differences over all time points. Using histograms, variable distributions will be assessed to decide which link function to specify when modeling each outcome. To account for the inherent correlation that occurs in repeated measures data, we will cluster on subject ID. In addition to

examining the unadjusted relationship between the time-treatment interaction and each outcome, we will consider the addition of control variables, which will reduce the likelihood of unaccounted confounders. The control variables being considered for inclusion in the adjusted models are age, sex, and disease duration. For each outcome, models will be fit for all possible combinations of control variables. The predictor set that yields the smallest Akaike information criterion (AIC) will be considered the optimal control variable set to adjust associations between the main predictor and the outcomes. Statistical significance will be assessed at the $\alpha = 0.05$ level.

XI.2

Provide the rationale or power analysis to support the number of subjects proposed to complete this study.

The sample size calculation was based on the Fatigue Severity Scale data from our own preliminary data that assessed the effects of multiple sessions of 4 mA tDCS on fatigue in people with multiple sclerosis. The effect size of this difference = 0.91 (Cohen's d). With alpha fixed at 0.05, we would need 20 total subjects in each group (tDCS and SHAM; details below) to achieve 80% power in a two-tailed independent samples test. Therefore, to account for 20% data and subject attrition, we will recruit 25 subjects per group (150 total).

XII. Future Research

XII.1

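### Section XI.1 tests every fatigue and quality-of-life measure over all time points at 0.05, with no primary outcome, primary visit or multiplicity rule; the FSS comparison that sized the trial has no protected status

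*Combined protocol and SAP*

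**What the plan says.** Section XI.1 applies GEE to the fatigue and quality-of-life measures as a set. On the tests it says: "An interaction term between time and treatment will allow us to test the within- and between-treatment differences over all time points". The threshold is 0.05 and no adjustment is mentioned. The model is partly open. The link for each outcome is chosen from histograms. Besides "examining the unadjusted relationship between the time-treatment interaction and each outcome, we will consider the addition of control variables", namely age, sex and disease duration. "For each outcome, models will be fit for all possible combinations of control variables", and the smallest AIC decides the set.

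Section XI.2 is more specific: "The sample size calculation was based on the Fatigue Severity Scale data from our own preliminary data". With d = 0.91 it asks for 20 per group "to achieve 80% power in a two-tailed independent samples test", and 25 per group after 20% attrition. It does not call FSS primary and gives no visit.

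Section I.5 states Hypothesis 1 as "Fatigue and QOL will significantly improve immediately after five consecutive sessions of M1 tDCS". Hypothesis 2 puts the same improvements at 3 and 6 weeks. Neither is ranked above the other.

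Section VII.E.6 lists two fatigue scales on Day 1, FAS and FSS. The battery is repeated on Day 5 and three and six weeks after Day 5, which makes three post-baseline visits. Section VII.B.11 asks "Is there a separate, written protocol that will be submitted in addition to this IRB New Project form"; the answer is no.

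**The concern.** The hypotheses are worded as claims of significant improvement in a randomised, sham-controlled trial. If XI.1 is followed as written, any scale at any visit that falls below 0.05 can be reported as a tDCS effect. The one comparison the trial was sized for, tDCS against sham on FSS, stands on the same footing as all the others. The probability of some false claim is then above 5% even when each single test has exactly its nominal size. A reader of the results could not tell the planned comparison from the most favourable one.

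**Working it through.** **1. The plan's own figure.** Inputs from XI.2: d = 0.91, two-sided alpha 0.05, power 80%, independent samples, 20% attrition. The two-sample t test with noncentrality d × √(n/2) needs n = 19.96 per group, so 20. At n = 20 the noncentrality is 0.91 × √10 = 2.88 and the power is 80.1%. Attrition: 20 / (1 − 0.20) = 25. XI.2 is reproduced, for one FSS comparison.

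**2. Counting the between-arm tests.** Two fatigue scales × three post-baseline visits (Day 5, 3 weeks, 6 weeks) = 6. If XI.1 instead means one joint time-by-treatment test per scale, there are 2. If FSS alone is meant, there are 3 visit tests.

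**3. Independent tests.** P(at least one false positive) = 1 − 0.95^m.

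- m = 6: 1 − 0.95^6 = 26.5%
- m = 3: 1 − 0.95^3 = 14.3%
- m = 2: 1 − 0.95^2 = 9.75%

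**4. Correlated tests.** The documents give no correlations, so these are assumptions, shown as a range. Six two-sided 0.05 z tests, 1,000,000 simulated draws per cell:

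| Between-scale correlation | Between-visit 0.3 | 0.5 | 0.7 | 0.8 |
|---|---|---|---|---|
| 0.3 | 24.9% | 22.9% | 20.1% | 18.2% |
| 0.5 | 23.7% | 21.9% | 19.2% | 17.3% |
| 0.7 | 22.0% | 20.2% | 17.7% | 15.9% |
| 0.8 | 20.7% | 19.0% | 16.6% | 14.9% |

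Simulated t tests at 20 per arm agree. Change from baseline gives about 18-23% for between-scale correlation 0.3-0.8 and within-subject correlation 0.5-0.7; post-baseline values alone give about 17-23%. With the independent case as the upper limit, the range is about 15-26%.

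**5. One joint test per scale.** Simulated 3-df tests on the three changes from baseline (20 per arm, 20,000 null trials per setting) give about 8.7% at between-scale correlation 0.7 and about 7.5% at 0.9. The independent limit is 9.75%. Range: about 7-10%.

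**6. FSS alone at three visits.** Changes from a shared baseline, with equal within-subject correlation, correlate 0.5 between visits. Three z tests give 13.2%, 12.5% and 11.8% at correlations 0.4, 0.5 and 0.6, so about 12-13%.

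**7. Power under the alternatives.** One primary test keeps 80.1% at 20 evaluable per arm. Bonferroni over six tests uses 0.05/6 = 0.0083, and power falls to 54.3%. Restoring 80% would take 31.03, so 32 evaluable per arm, or 32 / 0.80 = 40 recruited.

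**8. Gating.** In simulated null trials, a primary at 0.05 followed by Holm on the rest at a separate 0.05 without a gate gave 7.4-9.6% overall. With Holm run only after a significant primary, it gave about 5% (4.7-5.3%).

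**The case against.** The strongest reply is that XI.1 speaks of a single interaction term, so one joint test per outcome is a natural reading. That stands: the documents do not say whether testing is joint or visit by visit. A reader might infer that the plan carries a fixed error rate of 20% or more. It does not support that, because such a figure needs visit-by-visit testing and assumed correlations. Even so, the joint reading with two scales exceeds 5%.

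Second, XI.2 may be taken to make FSS primary by implication. Even then no visit is chosen, and three visits at 0.05 give about 12-13%.

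Third, the negative answer in VII.B.11 might be read as proof that no document names a primary. That goes too far, because the question itself sets grant applications aside and VII.A.10 mentions a pilot grant. What can be said is that nothing in this document names one. Pilot funding also makes an exploratory label reasonable, and that would be an acceptable answer.

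Fourth, a reader might infer that fitting unadjusted and adjusted models doubles the tests. With complete data, an identity link and an exchangeable GEE, adding three time-invariant covariates changed the Day 5 interaction p-value by less than 1e-14. AIC is also a definite rule for the adjusted model. But with 20% attrition the two p-values differed by up to 0.13, and XI.1 does not say which one decides. The case for fixing one model in advance therefore stands.

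**Conclusion.** The gap is real and should be closed. XI.1 tests several measures over several visits at 0.05 and singles out none; XI.2 and I.5 do not fill the gap. For FAS and FSS the chance of at least one false positive is about 15-26% visit by visit and about 7-10% with one joint test per scale. FSS alone at three visits gives about 12-13%. These figures assume correctly sized tests and correlations that the documents do not supply; the conclusion that the rate exceeds 5% holds throughout the range examined. They count between-arm tests on two scales only. The within-arm tests and any quality-of-life measure are left out and would add further opportunities for error.

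The documents do not support inferring that XI.2 is wrong: its arithmetic is correct for a single comparison. Nor do they support treating Day 5 as the obvious primary visit under Hypothesis 1. I.5 speaks of five sessions before the assessment. VII.E.6 gives a first round on Day 1 and stimulation on the following four days, yet says subjects do not receive tDCS on Day 5. VII.E.19 pays for four stimulation sessions ($15 each, $60 in total).

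**What to change.** In XI.1:

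1. Name one primary test at two-sided 0.05: the tDCS-sham contrast on FSS in the COVID-fatigue group, at one pre-specified post-baseline visit, from one pre-specified model with its link and covariate set fixed in advance.
2. Test the other outcomes and visits by Holm only if the primary is significant, or label them exploratory. Labelling all results exploratory, with no confirmatory claim, is also acceptable.
3. Before fixing the visit, reconcile I.5, VII.E.6 and VII.E.19 on how many stimulation sessions precede the Day 5 assessment.
4. Reconcile VI.13 and VII.E.2, which randomise 25 per arm in all three populations, with VII.E.6, where asymptomatic subjects attend one session only. Who is randomised and who contributes repeated measures depends on this.

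The cost is wording, with no extra subjects and no loss of XI.2's power at 20 evaluable per arm. The downside is that secondary outcomes and visits lose confirmatory status unless the primary succeeds.
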